#### **4.2.4. Long-Term Follow-Up (LTFU) Phase – IM Regimen Only**

Any participant who receives at least a single dose of CAB LA and/or RPV LA and discontinues the CAB LA + RPV LA regimen for any reason must remain on suppressive HAART for at least 52 weeks after the last dose of CAB LA and/or RPV LA in order to prevent the potential selection of INI- and/or NNRTI-resistant mutants.

**Investigators must discuss the choice of the follow-up HAART regimen with the Medical Monitor prior to initiating the new regimen with the participant. HAART therapy should be initiated within 4 weeks of the last injection**

The LTFU will begin the day of the last CAB LA and/or RPV LA dose and continue for 52 weeks, or until CAB LA + RPV LA is locally approved and commercially available. These participants will not complete a Withdrawal visit, but will instead move directly into the Long-Term Follow-Up Phase as per the Time and Events Schedule.

Participants will be assessed with clinic visits at months 1, 3, 6, 9 and 12 during the Follow-Up Phase. Female participants of child bearing potential must continue to use adequate contraception methods (see Study Procedures Manual [SPM] for list of accepted forms of contraception) for at least 52 weeks after the last injection.

In order to assure that participants have access to HAART during the Long-Term Follow-Up Phase, GSK may supply HAART regionally or reimbursement will be provided as needed during this phase. As participants approach the end of the Long-Term Follow-Up Phase (e.g., Prior to Month 12 visit), investigative sites and/or participants must make alternative arrangements for independent access of the participant's continued HAART off / post study.

The Long-Term Follow-Up Phase may be shortened at any time during the study for various reasons; e.g., better understanding of risks of development of resistance as CAB and RPV exposures decline, regulatory approval and commercial availability, end of study timings, etc.

This phase is considered study participation and participants will be followed on study during this time. A withdrawal visit is not required for participants who do not complete the Long-Term Follow-Up Phase. The participants' last on study visit will be considered as their withdrawal visit.

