To assess degree of health-related quality of life (HRQoL)	
 
● Change from Baseline in HR QoL using the HIV/AIDS-targeted quality of life questionnaire (HAT QoL) short form at Week 24, Week 48, Week 96 (or Withdrawal).
 

To assess the health status	
 
● Change from Baseline in health status at Week 24, Week 48, and Week 96 (or Withdrawal) using the 12-item Short Form Survey (SF-12).
 

To assess treatment satisfaction of CAB LA + RPV LA compared to continuation of current ART	
 
● Change from baseline in total “treatment satisfaction” score, and individual items scores of the HIVTSQs at Weeks 4b, 24, 44, 96 (or Withdrawal)
 
● Change in treatment satisfaction over time using the HIVTSQc at Week 48 (or Withdrawal)
 

To assess treatment acceptance	
 
● Change from Baseline in treatment acceptance at Week 8, Week 24, Week 48, Week 96 (or Withdrawal) using the “General acceptance” dimension of the Chronic Treatment Acceptance (ACCEPT)
 

Objectives	Endpoints
	questionnaire
To assess tolerability of injections	
 
Change from Week 4b in tolerability of injection at Week 5, Week 40, Week 41, and Week 96 using the Numeric Rating Scale (NRS) within the CAB + RPV LA arm.
 

Exploratory	
To explore the effect of patient characteristics (e.g., demographic factors, Baseline CD4+) on the virologic and immunologic responses to CAB LA+ RPV LA compared to continuation of current ART	
 
Proportion of participants by patient subgroup(s) (e.g., by age, gender, BMI, race, HIV-1 subtype, Baseline CD4+) with Virologic Failure over time including Week 48 using the Snapshot algorithm for the ITT-E population
 
Proportion of participants by patient subgroup(s) (e.g., by age, gender, body mass index (BMI), race, HIV-1 subtype, Baseline CD4+) with plasma HIV-1 RNA <50 c/mL over time including Week 48 using the Snapshot algorithm for the ITT-E population
 
Change from Baseline in CD4+ cell counts by subgroups at Week 48
 

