**Participants must be discontinued from the study for any of the following reasons:**

- Participants who are not eligible to continue into the Maintenance Phase.
- Participants who are not eligible, or do not wish to continue on to the Extension Phase.
- Virologic withdrawal criteria as specified in Section 5.5.4 are met;
- For participants in the current ART arm during the Maintenance Phase, plasma HIV-1 RNA  $\geq 50$  c/mL at Week 48 with a confirmatory retest;
- Participant requires substitution or dose modification of current ART;
- Participant requires substitution or dose reduction of CAB LA or RPV LA (oral bridging supply and potential for a second loading dose may be permissible following discussion with the Medical Monitor).
- Liver toxicity where stopping criteria are met and no compelling alternate cause is identified (see Section 5.5.1);
- Renal toxicity are met and no compelling alternate cause is identified;
- QT interval (QTc) interval  $> 550$  msec from three or more tracings separated by at least 5 minutes and considered causally related to IP.
- Grade 4 clinical AE considered causally related to study drug;
- Participant has a Grade 3 or higher rash or Grade 2 rash with evidence of systemic involvement and no compelling alternative cause is identified
- Pregnancy (intrauterine), regardless of termination status of pregnancy.
- Participant withdrew consent

Efficacy data for participants withdrawing from the study will be considered evaluable up to the point at which they are withdrawn using the same criteria for evaluability as for participants who complete the study.

Safety data for all participants who receive any amount of study drug, including participants who withdraw from the study, will be included in evaluations of safety.

If a participant is prematurely or permanently withdrawn from the study, the procedures described in the Time and Events Table for the in-clinic Withdrawal visit are to be performed. An in-clinic Follow-Up visit will be conducted 4 weeks after the last dose of study medication for participants with ongoing AEs, and serious adverse events (SAEs)

related & not related to study drug and also any laboratory abnormalities that are considered to be AEs or potentially harmful to the participant, at the last on-study visit.

All data from the Withdrawal visit will be recorded, as they comprise an essential evaluation that should be done prior to discharging any participant from the study.

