**Sites should contact the Medical Monitor to discuss individual participants, whenever necessary.**

#### **5.5.5.3. Confirmed Virologic Failure**

Participants who confirm virologic failure must be discontinued from the study. However, participants who have received at least one dose of CAB LA or RPV LA prior to confirming virologic failure will remain in the study on oral HAART in the Long-Term Follow-Up Phase (see Section 4.2.4).

A plasma sample from the suspected virologic failure visit as well as Day 1 (Baseline) will be sent for genotypic and phenotypic resistance testing and the result made known to the Investigator when available. A plasma sample from the confirmation visit will be obtained for storage. This sample may be used for possible future analyses, e.g., for genotypic and phenotypic analyses of participants who experience virologic failure. See Section 7.8 for additional details for viral genotyping and phenotyping.

For all participants who meet CVF, baseline and suspected virologic failure plasma samples with HIV-1 RNA level  $\geq 200$  c/mL will be analyzed in an attempt to obtain genotype/phenotype data on as many samples as possible. Plasma samples for storage will also be obtained at unscheduled visits including confirmation of CVF. Participants may continue to receive study drug at the discretion of the investigator until results of resistance testing are available at which time the participant must be discontinued from the study. Even if genotype/phenotype data cannot be generated, participant must also be discontinued from the study.

If a participant is prematurely discontinued from the study, the investigator must make every effort to perform the Withdrawal Visit evaluations outlined in the Time and Events Section 7.1. These data will be recorded as they comprise essential evaluations needed to be done before discharging any participant from the study.

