- v. With the exception of the NRS questionnaire, all Patient Report Questionnaires/Surveys are recommended to be administered via validated electronic site pad or paper instrument at the beginning of the visit before any other assessments are conducted and prior to administration of the eC-CSSRS. NRS is to be given post injection. Conduct questionnaires/surveys at Withdrawal if occurring prior to Week 96.
- w. HIV TSQ (c) to be administered at Week 48 to LA injection arm only
- x. "Reason for switch" will be administered prior to randomization at Day 1. At Week 52, "Reason for Switch" will be given only to participants randomized to the "Current ART" arm.
- y. "Preference" question to be administered at Week 48 to patients randomized to CAB LA + RPV LA arm, and at Week 96 to patients randomized to the "current ART arm" who switched to CAB LA + RPV LA at the end of maintenance phase.
- z. NRS will be administered on injection visits approximately 30-60 minutes following injections. Participant should record the maximum level of pain experienced with the most recent injections.

Note: BP – Blood pressure, HR – Heart Rate, HDL – High Density Lipoprotein, LDL – Low Density Lipoprotein, PT Prothrombin Time, PTT Partial Thromboplastin Time, INR International normalized ratio

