### 9.3.2.3. Secondary comparisons

The following key secondary comparison will be tested:

- Treatment with CAB LA + RPV LA will be declared non-inferior to current ART if the lower end of a two-sided 95% confidence interval for the difference between the two groups in response rates at Week 48 lies above -10%.
- Superiority of CAB LA + RPV LA compared to continuation of current ART with respect to change from baseline HIVTSQs total score at Week 44;
- Changes in the PIN acceptance score within the CAB LA + RPV LA arm from Day 4 to Week 48

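### Conflicting rules on exit assessment after an injection could leave exit questionnaires collected mainly in the control arm, and HIVTSQc has no control data at Week 48 despite a comparative objective

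*Protocol*

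**What the plan says.** **Exit visit.** Section 4.2.4, like the Synopsis, covers anyone who discontinues after at least one dose of CAB LA and/or RPV LA: "These participants will not complete a Withdrawal visit, but will instead move directly into the Long-Term Follow-Up Phase". Other sections point the other way:

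- Section 5.5, for a premature or permanent withdrawal from the study: "the procedures described in the Time and Events Table for the in-clinic Withdrawal visit are to be performed".
- Section 5.5.5.3, at the end of the confirmed virologic failure rules: "the investigator must make every effort to perform the Withdrawal Visit evaluations outlined in the Time and Events Section 7.1".
- Sections 7.4.3.11 and 7.4.3.12 ask for, or encourage, withdrawal evaluations after a Grade 3 or Grade 4 event that ends treatment. The same bullets send injected participants to long-term follow-up (LTFU).
- Table 8 in Section 7.5.1 lists a Withdrawal PK sample for participants receiving the injections.

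**Questionnaires.** Section 3 defines the HIVTSQs, HIVTSQc, ACCEPT, SF-12 and HAT-QoL endpoints at fixed weeks or at withdrawal. Footnote v of the Time and Events Table adds: "Conduct questionnaires/surveys at Withdrawal if occurring prior to Week 96". No questionnaire endpoint names an LTFU time point. Section 9.3.2.3 lists, among the key secondary comparisons, superiority of CAB LA + RPV LA "with respect to change from baseline HIVTSQs total score at Week 44".

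**HIVTSQc.** Section 3 places it under the objective "To assess treatment satisfaction of CAB LA + RPV LA compared to continuation of current ART". Footnote w says: "HIV TSQ (c) to be administered at Week 48 to LA injection arm only".

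**The concern.** A participant who gives up injections is an obvious candidate for a low satisfaction score. If 4.2.4 governs, that participant leaves treatment without an exit questionnaire, while a participant who leaves the current ART arm completes one. The trial is open-label and treatment satisfaction is a key secondary comparison, so a difference between arms in what is collected deserves attention.

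This is not a matter that the analysis plan can settle. Section 9.4.7 leaves the missing-data method to the RAP, which is normal, but the protocol decides what is collected. A RAP can make assumptions about stoppers; it cannot supply scores that were never taken.

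The HIVTSQc problem is separate. An endpoint listed under a between-arm objective has no control-arm value at its stated week.

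**Working it through.** **Step 1. What each group yields if 4.2.4 is followed.**

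| Participant who stops before Week 96 | Withdrawal visit? | Exit questionnaires? |
|---|---|---|
| Current ART arm | Yes (5.5) | Yes (footnote v) |
| LA arm, stops in the oral lead-in | Yes (no injection yet) | Yes |
| LA arm, stops after an injection | No (4.2.4) | None named |

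PIN shows the effect most plainly. Only injected people can answer it and it appears to carry a mark at Withdrawal, yet under 4.2.4 injected people have no such visit.

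**Step 2. What an injected stopper still contributes to HIVTSQs.** The instrument is scheduled at baseline, Weeks 4b, 24, 44 and 96. Footnote v puts questionnaires at the start of the visit, so the Week 4b score precedes the first injection. Someone who stops between Week 4b and Week 24 therefore has no HIVTSQs score that reflects injections. Someone who stops between Weeks 24 and 44 has one, at Week 24.

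**Step 3. Possible size.** The protocol gives no SD, effect size or power for HIVTSQs, so it has no figure of its own to reproduce.

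Inputs: 285 per arm (Section 9.2.1). As a stand-in for LA discontinuation, LATTE-2 Q4W had 9 of 115 with no virologic data at Week 48 (Table 2): 9/115 = 7.8%, and 0.078 × 285 ≈ 22. Assumptions: a stopping share d of 3% to 12%; a fall D in stoppers' satisfaction of 0.25 to 1.5 SD; a test at one-sided 2.5%.

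*Scenario A: Withdrawal values enter the Week 44 analysis.* Control stoppers' falls are recorded. For LA stoppers an earlier on-treatment value stands in. Then

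- bias toward LA = d × D (SD units)
- SE of the difference = √(2/285) = 0.084 SD
- one-sided error = 1 − Φ(1.96 − bias/SE)

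For example, with d = 7.8% and D = 0.5: bias = 0.039 SD = 0.47 SE, and error = 1 − Φ(1.49) = 6.8%.

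| d (stoppers of 285) | D = 0.25 | D = 0.5 | D = 1.0 | D = 1.5 |
|---|---|---|---|---|
| 3% (9) | 0.007 SD; 3.1% | 0.015; 3.7% | 0.030; 5.5% | 0.045; 7.7% |
| 7.8% (22) | 0.020; 4.2% | 0.039; 6.8% | 0.078; 15.3% | 0.117; 28.8% |
| 12% (34) | 0.030; 5.5% | 0.060; 10.7% | 0.120; 29.9% | 0.180; 57.5% |

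For scale, 285 per arm gives 90% power for (1.96 + 1.28) × 0.084 = 0.27 SD.

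*Scenario B: only observed Week 44 scores are used.* Stoppers are absent from both arms. Each arm's mean is overstated by its loss times its gap, so the net effect on the difference is d(LA) × D(LA) − d(control) × D(control). The LATTE-2 oral arm lost 5/56 = 8.9% (Table 2). With equal gaps the net is (0.078 − 0.089) × D = −0.011 × D: close to zero and slightly against LA. Here the exit-visit rule plays no part.

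**Step 4. HIVTSQc.** Week 48 values come from the LA arm alone. The Withdrawal mark for HIVTSQc carries no arm limit, so if 4.2.4 is followed the Withdrawal values come from controls and from LA participants who stop before an injection. No week has values from both arms as randomized.

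**The case against.** **The sections might be harmonised.** Sections 5.5 and 5.5.5.3 speak of leaving the study, and 5.5.5.3 keeps injected participants with virologic failure in the study through LTFU, so 4.2.4 could be read as the specific rule. This does not hold throughout. Section 5.6 counts people who enter LTFU as prematurely withdrawn from the study, Sections 7.4.3.11 and 7.4.3.12 attach withdrawal evaluations to stopping treatment, and Table 8 expects a Withdrawal sample from LA recipients. If the reading did hold, the difference between arms would simply be the rule.

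**The last LTFU visit counts as the withdrawal visit.** Section 4.2.4 says so for people who do not complete LTFU. That visit can fall months later on a different regimen, and an added HIVTSQ item asks about the present form of treatment (Section 7.9). It would not be an exit score for CAB LA + RPV LA. The same caution applies to LTFU Month 1, because 4.2.4 has replacement HAART starting within 4 weeks of the last injection.

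**Stronger readings.** A reader might infer that the satisfaction comparison cannot be made. The documents do not support that: the key secondary test uses HIVTSQs at Week 44, scheduled in both arms with no footnote limiting it to one. A reader might also infer that the comparison favours CAB LA + RPV LA. That depends on the unseen missing-data method, on how many stop in each arm and on how their satisfaction changes; Scenario B shows the sign can differ. The count of 22 also overstates the group affected at that rate, since stops in the oral lead-in or after Week 44 do not belong to it. These objections stand against any claim of demonstrated bias, but not against the contradiction.

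**HIVTSQc is meant for people who changed treatment.** This is fair. Section 7.9 describes comparing current with previous satisfaction in the same participants, and controls have not switched by Week 48. What remains is that it is listed under a comparative objective.

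**Conclusion.** The concern stands in a limited form. The protocol gives incompatible instructions on end-of-treatment evaluation for participants who stop after an injection, and its questionnaire endpoints depend on the visit in dispute. Followed as 4.2.4 is written, exit scores are collected from current ART stoppers and lead-in stoppers but not from injected stoppers, and the PIN Withdrawal assessment cannot take place in the people it is meant for.

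The effect on between-arm questionnaire results is possible, not established. If Withdrawal values enter the Week 44 HIVTSQs analysis, and 7.8% of the LA arm stop with an unrecorded fall of 0.25 to 1.5 SD, the shift is 0.02 to 0.12 SD toward LA. Those falls are assumptions, and the stopping rate is borrowed from another trial. In an observed-only Week 44 analysis the mechanism does not operate.

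For HIVTSQc no randomized comparison is possible at Week 48, so the endpoint does not match its objective. Both defects should be corrected.

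**What to change.** 1. Reconcile Section 4.2.4 and the Synopsis with Sections 5.5, 5.5.5.3, 7.4.3.11 and 7.4.3.12 and with Table 8, so that one rule governs end-of-treatment evaluations for injected participants.
2. State that the Withdrawal questionnaires (HIVTSQs, HIVTSQc and PIN where applicable, ACCEPT, SF-12, HAT-QoL) are completed in both arms at the visit where stopping is decided and, for LA participants, before the replacement regimen starts. This concerns the timing of the questionnaires only, not of treatment.
3. If a score is first obtained at LTFU Month 1, flag it as taken after the switch and do not treat it as a score on CAB LA + RPV LA.
4. Move HIVTSQc to a within-LA-arm objective, or give it to both arms at the existing Week 48 visit.

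The cost is a text and footnote change and a few minutes of questionnaires at an existing visit.

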#### **4.2.5. Dose Modifications**

No dose reductions, modifications, or changes in the frequency of any components of each regimen will be allowed during the study. Protocol waivers or exemptions are not allowed. Therefore, adherence to the study design requirements is essential and required for study conduct.

In exceptional circumstances, and in consultation with the Medical Monitor, Investigators may provide oral CAB and/or RPV as a short-term "bridging" strategy for participants who have begun CAB LA + RPV LA. Should a participant need "oral bridging", sites must contact the Medical Monitor for guidance on treatment strategies prior to a missed CAB LA + RPV LA dose. Should a participant not notify the site in advance, the Medical Monitor must be contacted for further treatment guidance. See Section 6.8.1 for additional information on oral bridging.

#### **4.3. 207966 (ATLAS-2M) Rollover Option**

The 207966 (ATLAS-2M) study is being conducted in approximately 1020 participants to establish if human immunodeficiency virus type 1 (HIV-1) infected adults with current viral suppression (HIV-1 RNA <50 c/mL) remain suppressed upon administration of a two-drug intramuscular (IM) long-acting (LA) regimen of cabotegravir (CAB) and rilpivirine (RPV) administered every 8 weeks (Q8W; every 2 months). The ATLAS-2M study is designed to demonstrate the non-inferior antiviral activity of CAB LA 600 mg + RPV LA 900 mg administered every 8 weeks compared with CAB LA 400 mg + RPV LA 600 mg administered every 4 weeks (Q4W; monthly) over a 48-week treatment period. ATLAS-2M will also provide comparative data on antiviral activity, safety, tolerability, and patient satisfaction through Week 96. It is anticipated that the majority of ATLAS participants will transition to the ATLAS-2M study

Upon local approval and implementation of the ATLAS-2M trial, investigators will approach all potentially eligible ATLAS participants with the optional consent for ATLAS-2M participation and potential randomization to the CAB LA + RPV LA Q4W

or Q8W regimen. If a participant cannot or chooses not to transition to the ATLAS-2M trial, or is otherwise determined to be ineligible for ATLAS-2M, the participant can elect to continue participation in ATLAS trial without limitations and according to the approved protocol design.

Eligibility to transition to ATLAS-2M at Week 52 (at the earliest) will be determined once the final central lab results from ATLAS, following (at minimum) completion of the ATLAS Week 48 visit are available and safety parameters have been reviewed. Separate Screening Labs will be utilized to inform eligibility for ATLAS-2M; however, in some occasions and upon consultation with the Medical Monitor, individual lab results and safety data from the final visit of the ATLAS study can be considered towards informing eligibility for the ATLAS-2M study as long as all other screening and eligibility criteria are met.

#### **4.3.1. 201585 (ATLAS) to 207966 (ATLAS-2M) Transition Strategy**

Upon the final ATLAS on-study visit (ATLAS Week 52 or later), which overlaps with the Day 1 Baseline visit for ATLAS-2M, all procedures and assessments must be performed and recorded as per both individual study Time and Events Tables with the exception that participants will receive only the scheduled Day 1 ATLAS-2M treatment (participants will not receive the corresponding ATLAS study treatment).

ATLAS participants on current ART therapy who transition to ATLAS-2M at the ATLAS Week 52 visit, will begin a 4 week oral lead-in treatment with CAB 30 mg + RPV 25 mg once daily, per the ATLAS-2M Time and Events table. Participants currently receiving CAB LA + RPV LA Q4W at the overlapping visit (including those who were originally randomized to the Q4W regimen and those who more recently switched to the Q4W regimen within the Extension Phase of ATLAS) will continue CAB LA + RPV LA Q4W or initiate CAB LA + RPV LA Q8W treatment as per the ATLAS-2M randomized treatment schedule.

Following the baseline Day 1 visit for ATLAS-2M, participants will follow all schedules and activities of the ATLAS-2M trial. No withdrawal visit nor long-term follow up phase participation for ATLAS is required. An in-clinic Follow-Up visit (which may or may not overlap with an ATLAS-2M visit) will be conducted approximately 4 weeks after the last dose of ATLAS study medication for participants with ongoing AEs, and serious adverse events (SAEs) related & not related to study drug and any laboratory abnormalities that are considered to be AEs or clinically significant at the last ATLAS on-study visit.

